9.2 Study Discontinuation and Closure

This study may be temporarily suspended or prematurely terminated if there is sufficient reasonable cause. Written notification, documenting the reason for study suspension or termination, will be provided by the suspending or terminating party to study participants, investigator, funding agency, sponsor, and regulatory authorities. If the study is prematurely terminated or suspended, the Principal Investigator (PI) will promptly inform study participants, the Institutional Review Board (IRB), and sponsor and will provide the reason(s) for the termination or suspension. Study participants will be contacted, as applicable, and be informed of changes to study visit schedule.

Circumstances that may warrant termination or suspension include, but are not limited to:

- Determination of unexpected, significant, or unacceptable risk to participants
- Demonstration of efficacy that would warrant stopping
- Insufficient compliance to protocol requirements
- Data that are not sufficiently complete and/or evaluable
- Determination of futility

Study may resume once concerns about safety, protocol compliance, and data quality are addressed, and satisfy the sponsor, IRB and/or Food and Drug Administration (FDA).

9.3 Confidentiality and Privacy

Participant confidentiality and privacy is strictly held in trust by the participating investigators, their staff, and the sponsor(s) and their interventions. This confidentiality is extended to cover testing of biological samples and genetic tests in addition to the clinical information relating to participants. Therefore, the study protocol, documentation, data, and all other information generated will be held in strict confidence. No information concerning the study or the data will be released to any unauthorized third party without prior written approval of the sponsor.

All research activities will be conducted in as private a setting as possible.

The study monitor, other authorized representatives of the sponsor, representatives of the Institutional Review Board (IRB), or regulatory agencies may inspect all documents and records required to be maintained by the investigator, including but not limited to, medical records (office, clinic, or hospital) and pharmacy records for the participants in this study. The clinical study site will permit access to such records.

The study participant's contact information will be securely stored at each clinical site for internal use during the study. At the end of the study, all records will continue to be kept in a secure location for as long a period as dictated by the reviewing IRB, Institutional policies, or sponsor requirements.

Study participant research data, which is for purposes of statistical analysis and scientific reporting, will be transmitted to and stored at the Data Coordinating Center. This will not include the participant's contact or identifying information. Rather, individual participants and their research data will be identified by a unique study identification number. The study data entry and study management systems used by clinical sites and by the Data Coordinating Center research staff will be secured and password protected. At the end of the study, all study databases will be de-identified and archived at the Data Coordinating Center at UCSF.

9.3.1 CERTIFICATE OF CONFIDENTIALITY

To further protect the privacy of study participants, a Certificate of Confidentiality will be issued by the National Institutes of Health (NIH). This certificate protects identifiable research information from forced disclosure. It allows the investigator and others who have access to research records to refuse to disclose identifying information on research participation in any civil, criminal, administrative, legislative, or other proceeding, whether at the federal, state, or local level. By protecting researchers and institutions from being compelled to disclose information that would identify research participants, Certificates of Confidentiality help achieve the research objectives and promote participation in studies by helping assure confidentiality and privacy to participants.

9.4 Future Use of Stored Specimens and Data

Data collected for this study will be analyzed and stored at the Data Coordinating Center at UCSF. After the study is completed, the de-identified, archived data will be transmitted to and stored on the Research Electronic Data Capture system (REDCap).

With the participant's approval and as approved by local Institutional Review Boards (IRBs), de-identified biological samples will be stored at the enrollment site.

During the conduct of the study, an individual participant can choose to withdraw consent to have biological specimens stored for future research. However, withdrawal of consent with regard to biosample storage may not be possible after the study is completed.

When the study is completed, access to study data will be provided through REDCap.

10.1 Safety Oversight

A Data and Safety Monitoring Committee (DSMC) will be empaneled by the NEI. The committee will meet in person at least once per year and will convene biannual teleconferences for progress reports. *Ad hoc* meetings as needed may also be convened. The committee will review information on data quality, enrollment, patient retention, and study outcomes, etc. Committee members will be unmasked and receive reports of the data with ARM information at one interim time-point (when 1/3rd of the primary outcome has been collected). All study protocols will be subject to review and approval by Institutional Review Boards.

10.2 Clinical Monitoring

Clinical site monitoring is conducted to ensure that the rights and well-being of study participants are protected, that the reported study data are accurate, complete, and verifiable, and that the conduct of the study is in compliance with the currently approved protocol/amendment(s), with International Conference on Harmonisation Good Clinical Practice (ICH GCP), and with applicable regulatory requirement(s).

Clinical monitoring will be conducted by the Clinical Coordinating Center (CCC) at UCSF. One person will make site visits to all enrollment sites once a year to monitor study activities. During each visit the CCC will conduct a complete chart review of all patient charts to ensure data is being recorded in a complete fashion. The CCC will conduct regular off-site reviews of data entered at UCSF to ensure 100% data verification.

10.3 Quality Assurance and Quality Control

Each clinical site will perform internal quality management of study conduct, data and biological specimen collection, documentation and completion. An individualized quality management plan will be developed to describe a site's quality management.

Quality control (QC) procedures will be implemented beginning with the data entry system and data QC checks that will be run on the database will be generated. Any missing data or data anomalies will be communicated to the site(s) for clarification/resolution.

Following written Standard Operating Procedures (SOPs), the monitors will verify that the study is conducted and data are generated and biological specimens are collected, documented (recorded), and reported in compliance with the protocol, and applicable regulatory requirements (e.g., Good Laboratory Practices (GLP)).

The investigational site will provide direct access to all study related sites, source data/documents, and reports for the purpose of monitoring and auditing by the sponsor, and inspection by local and regulatory authorities.

11 DATA HANDLING AND RECORD KEEPING

11.1 Data Collection and Management Responsibilities

Data collection is the responsibility of the study staff at the site under the supervision of the site investigator. The investigator is responsible for ensuring the accuracy, completeness, legibility, and timeliness of the data reported.

All source documents should be completed in a neat, legible manner to ensure accurate interpretation of data.

Hardcopies of the study visit worksheets will be provided for use as source document worksheets for recording data for each participant enrolled in the study. Enrollment sites will upload these forms to Box.com, where the Data Coordinating Center at UCSF will access these forms for data entry. Data recorded in the electronic case report form (eCRF) derived from source documents should be consistent with the data recorded on the source documents.

Clinical data (including adverse events (AEs), concomitant medications, and expected adverse reactions data) and clinical laboratory data will be entered into Research Electronic Data Capture (REDCap), a 21 CFR Part 11-compliant data capture system provided by the Data Coordinating Center at UCSF. The data system includes password protection and internal quality checks, such as automatic range checks, to identify data that appear inconsistent, incomplete, or inaccurate. Clinical data will be double data-entered directly from the source documents.

11.2 Study Records Retention

Study documents should be retained for a minimum of 2 years. No records will be destroyed without the written consent of the sponsor, if applicable. It is the responsibility of the sponsor to inform the investigator when these documents no longer need to be retained.

11.3 Protocol Deviations

A protocol deviation is any noncompliance with the clinical trial protocol, ICH GCP, or MOP requirements. The noncompliance may be either on the part of the participant, the investigator, or the study site staff. As a result of deviations, corrective actions are to be developed by the site and implemented promptly.

It is the responsibility of the site investigator to use continuous vigilance to identify and report deviations within 7 working days of identification of the protocol deviation, or within 7 working days of the scheduled protocol-required activity. All deviations must be addressed in study source documents, reported to National Eye Institute Program Official and the Coordinating Center at UCSF. Protocol deviations must be sent to the reviewing Institutional Review Board (IRB) per their policies. The site investigator is responsible for knowing and adhering to the reviewing IRB requirements.

11.4 Publication and Data Sharing Policy

This study will be conducted in accordance with the following publication and data sharing policies and regulations:

National Institutes of Health (NIH) Public Access Policy, which ensures that the public has access to the published results of NIH funded research. It requires scientists to submit final peer-reviewed journal manuscripts that arise from NIH funds to the digital archive PubMed Central upon acceptance for publication.

This study will comply with the NIH Data Sharing Policy. In addition, every attempt will be made to publish results in peer-reviewed journals.

11.5 Conflict of Interest Policy

The independence of this study from any actual or perceived influence is critical. Therefore, any actual conflict of interest of persons who have a role in the design, conduct, analysis, publication, or any aspect of this trial will be disclosed and managed. Furthermore, persons who have a perceived conflict of interest will be required to have such conflicts managed in a way that is appropriate to their participation in the design and conduct of this study. The study leadership in conjunction with the National Eye Institute has established policies and procedures

for all study group members to disclose all conflicts of interest and will establish a mechanism for the management of all reported dualities of interest.

11.6 Additional Considerations

None

12 ABBREVIATIONS

AC	Anterior Chamber
AE	Adverse Event
ANCOVA	Analysis of Covariance
BID	Twice a day
BUN	Blood Urea Nitrogen
CBC	Complete Blood Count
CCC	Clinical Coordinating Center
CFR	Code of Federal Regulations
CMV	Cytomegalovirus
Cr	Creatinine
DCC	Data Coordinating Center
DSMC	Data Safety Monitoring Committee
eCRF	Electronic Case Report Forms
FDA	Food and Drug Administration
GLP	Good Laboratory Practices
HIV	Human Immunodeficiency Virus
HSV	Herpes Simplex Virus
ICH	International Conference on Harmonisation
IOP	Intraocular Pressure
IRB	Institutional Review Board
MOP	Manual of Operations and Procedures
NEI	National Eye Institute
NIH	National Institutes of Health
OHRP	Office for Human Research Protections
PCR	Polymerase Chain Reaction
PI	Principal Investigator
PO	By mouth
QA	Quality Assurance
QC	Quality Control
REDCap	Research Electronic Data Capture
SAE	Serious Adverse Event
SAP	Statistical Analysis Plan
SMC	Safety Monitoring Committee
SOP	Standard Operating Procedure
UCSF	University of California, San Francisco
UP	Unanticipated Problem
US	United States
VA	Visual Acuity
VZV	Varicella-zoster Virus

VA	Visual Acuity
----	---------------

13 PROTOCOL AMENDMENT HISTORY

The table below is intended to capture changes of IRB-approved versions of the protocol, including a description of the change and rationale. A Summary of Changes table for the current amendment is located in the Protocol Title Page.

Version	Date	Description of Change	Brief Rationale

## 2. Introduction

### 2.1. Background and rationale

The systemic and topical antiviral control of cytomegalovirus anterior uveitis: treatment outcomes trial will enroll participants with PCR-proven CMV anterior uveitis into a sequential double-masked randomized clinical trial in the US and Asia. In Trial I, participants will be randomized to oral valganciclovir, topical ganciclovir 2%, or placebo and viral load after 7 days of treatment will be compared by arm. After participants achieve control of their inflammation, they will be offered enrollment to Trial II in which they will be re-randomized to one of the three arms in Trial I at prophylactic dosing and monitored for recurrence. Additionally, patients with known CMV anterior uveitis, but who are inactive, may enter Trial II directly. Recurrences of inflammation in Trial II will be assessed for presence of detectable viral load.

The purpose of this study is to identify the antiviral therapy best at reducing CMV load, assess use of long-term antiviral prophylaxis in decreasing recurrence, and examine the role of antiviral resistance mutations in CMV anterior uveitis.

### 2.2. Objectives

#### **Specific Aim 1 (Trial I): To compare CMV viral load and inflammation after randomization to oral valganciclovir, topical ganciclovir 2%, or placebo.**

*1a: We hypothesize that participants randomized to oral valganciclovir will have a lower viral load after 7 days compared to those randomized to either topical ganciclovir 2% or placebo (primary outcome).*

*1b: We hypothesize that a greater proportion of participants randomized to oral valganciclovir will have clinical inactivity at day 7 compared to those randomized to either topical ganciclovir 2% or placebo.*

*1c: We hypothesize RNA sequencing of aqueous humor fluid obtained as part of eligibility determination for Trial I, but negative for CMV, will identify other pathogens and provide host transcriptional profiling.*

#### **Specific Aim 2 (Trial II): To compare the effect of long-term antiviral suppression on recurrence rate of inflammation.**

*2a: We hypothesize that participants randomized to placebo will have fewer recurrences of inflammation over 12 months compared to those randomized to either oral valganciclovir or topical ganciclovir 2% (primary outcome).*

*2b: We hypothesize that aqueous obtained at the time of a recurrence of inflammation will demonstrate a detectable viral load and will correlate with level of inflammation.*

#### **Specific Aim 3 (samples from Trials I and II): To characterize host transcriptional signatures and viral genomic features in CMV anterior uveitis using RNA sequencing of aqueous samples.**

*3a: We hypothesize participants completing both trials who exhibit recurrent inflammation after antiviral suppression (Trial II) will have a higher prevalence of CMV mutations associated with antiviral resistance compared to baseline samples (Trial I).*

*3b: We hypothesize that host transcriptional profiles will (i) distinguish CMV anterior uveitis from anterior uveitis cases negative for CMV and unable to enter Trial I, (ii) we will identify non-CMV pathogens in cases unable to enter Trial I, and (iii) identify unique signatures associated with recurrent inflammation in Trial II participants.*

### 3. Study Methods

#### 3.1. Trial design

The trial is an individual sequential double-masked randomized placebo-controlled trial. In trial I, study subjects are randomized to three arms:

- 1) Oral valganciclovir
- 2) Topical ganciclovir 2%
- 3) Placebo

After achieving clinical quiescence, participants will be offered enrollment into Trial II where they will be randomized to one of the three arms:

- 1) Oral valganciclovir
- 2) Topical ganciclovir 2%
- 3) Placebo

#### 3.2. Randomization

For both trials, individuals will be randomized to the three arms in a 1:1:1 ratio. Randomization will be stratified by recruitment site, using randomly permuted blocks in multiples of 3 stratified, permuted block randomization will ensure that an approximately equal number of patients are randomized to each treatment arm by site. The masked allocation sequences will be generated at the UCSF Data Coordinating Center and implemented through a REDCap randomization module to ensure allocation concealment.

#### 3.3. Sample size

**Primary analysis for Trial I.** The power calculation was based on the primary outcome, base-10 logarithm-transformed CMV viral load. We informed the calculation with viral loads from our recently completed RCT, in which we measured viral load at baseline and 7 days post-treatment. The standard deviation (SD) of log-transformed viral load 7 days post-treatment in this RCT was 0.98. Since the primary analysis will adjust for baseline viral load, we used an estimate of the residual standard deviation, which is  $SD_r = SD\sqrt{1 - r^2}$ , where  $r$  is the correlation between the baseline measure and primary endpoint. In our recently completed RCT, the correlation between baseline and post-treatment viral load was 0.74. Assuming a significance level of 0.05/2=0.025 to account for multiple comparisons and an  $SD_r$  of 0.66 in  $\log_{10}$  viral load, we estimate that we will have 80% power to detect a difference of 0.50 in  $\log_{10}$  viral load (from

3.11 to 2.61) between arms with 35 study participants per arm (117 total allowing for approximately 10% loss to follow up). A reduction of 0.50 in  $\log_{10}$  viral load is equivalent to a  $10^{0.50} = 3.2$ -fold decrease in CMV viral load, which is small but clinically meaningful in the context of CMV antivirals that typically consider 10-fold reductions. This calculation is based on the standard power formula for the T-test using an estimated residual standard deviation.

**Primary analysis for Trial II.** The primary outcome for Trial II is the proportion of participants experiencing CMV recurrence over 12 months. We acknowledge that hypothesizing fewer recurrences in the placebo group compared to the oral antiviral group is contradictory to what one might think would typically occur with exposure to antivirals. However, data from a previous observational study showed a one-year recurrence risk of 25.0% (3/12) among participants who did not receive antiviral treatment and 75.0% (9/12) in participants receiving systemic antiviral treatment (oral ganciclovir or valganciclovir), which is similar to the experience of other research. Additionally, it is well documented that long-term suppressive-level dosing of antiviral in an immunodeficient host or in an immunologically privileged organ (such as the eye) can create an environment permissive to the development of antiviral resistance. Given 28 participants per arm (105 total from Trial I with 20% loss to follow-up) and a recurrence risk of 25% in the placebo group, we can detect a difference of 40 percentage points between the oral valganciclovir and the placebo groups (from 25% to 65%), using a two-sample z-test for proportions with 80% power and a two-sided alpha of 0.05/2.

**For Specific Aim 3,** we estimated the minimum detectable effect for the difference in prevalence of infections that have antiviral resistance mutations among recurrent infections in Trial II among patients who receive long-term antiviral prophylaxis compared with their infections at baseline. Aim 3 will focus on patients in the two active treatment arms in Trial II, because we would expect long-term use of topical and oral antivirals to lead to similar selection for antiviral resistance. From 117 patients enrolled, we conservatively assumed that 72% of patients would complete both Trial I and Trial II (n=84). We further assumed that 60% of patients will develop a recurrent infection over the monitoring period during the trials (Table 1). Participants who receive active treatment in Trial II (treatment regimens C+D) will contribute to the Aim 3 analysis (n=34). The analysis will be a paired analysis, comparing the proportion of recurrent infections with antiviral resistance mutations with that same proportion at baseline.

Table 1. Anticipated participant enrollment, and follow-up by treatment patterns

Treatment Pattern, Trial I → Trial II	Number enrolled	Number completing Trial I (assumed 90%)	Number completing Trial I and Trial II (assumed 80% from Trial I)	Number with Recurrent Infections in Trial II, included in Aim 3 (assumed 60%)
A. Placebo → Placebo	13	12	10	
B. Treatment → Placebo Topical g. → Placebo Oral v. → Placebo	26	23	18	
C. Placebo → Treatment Placebo → Topical g. Placebo → Oral v.	26	23	18	11
D. Treatment → Treatment Topical g. → Topical g. Topical g. → Oral v. Oral v. → Topical g. Oral v. → Oral v.	52	47	38	23
Total	117	105	84	34

In the absence of longer-term antiviral therapy, we anticipate 5% of patients would experience recurrent infections with antiviral resistance mutations. A recent analysis of 2750 transplant recipients identified 30.4% patient samples had resistance to anti-CMV drugs. We assumed 80% power and a two-sided alpha of 0.05. Under these assumptions, we estimate that we will be able to detect a 25% increase in the percentage of infections with antiviral resistance genes (from 5% to 30%), using a two-sample z-test for proportions with equal sample sizes. We note this detectable effect is conservative because it ignores possible correlation within-individuals in the paired outcomes, which would increase our power.

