## **4. Statistical Principles**

### **4.1. Confidence intervals and P-values**

The primary analysis for Trial I and Trial II will be conducted with a two-sided alpha of 0.05/2 = 0.025 to account for the two primary comparisons of interest (*oral valganciclovir* vs. *topical ganciclovir 2%*, *oral valganciclovir* vs. placebo). We will report 95% confidence intervals for the estimated differences between groups, on an absolute scale.

We will use a single-step, max-T approach to estimate p-values adjusted for multiple comparisons in each analysis. Alongside unadjusted p-values and 95% confidence intervals, we will present max-T adjusted p-values and simultaneous 95% confidence intervals for differences that account for multiple comparisons.

We will employ a multiple testing hierarchical approach in the following manner:

1. Primary endpointss (alpha = 0.025 each trial)
  - a. Trial I: viral load comparison
  - b. Trial II: Number of recurrences comparison
2. Key secondary endpoints (alpha = 0.025 shared):
  - a. Inflammation control
  - b. Antiviral resistance mutations

Gate-keeping procedure:

Primary endpoints must be significant before testing secondaries

Holm-Bonferroni correction within each family

Truncated testing if primary endpoint non-significant

Family-wise error rate controlled at 0.05 using:

Separate error rates for each trial

Sequential gatekeeping

Multiplicity adjustment within families

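### The Aim 3 power statement in SAP 3.3 is computed at a two-sided alpha of 0.05, but SAP 4.1 tests resistance mutations at 0.0125 or 0.025, where 80% power for a rise from 5% to 30% is not shown

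*SAP*

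**What the plan says.** SAP 3.3, in the Aim 3 text and Table 1, fixes the number of patients: "Participants who receive active treatment in Trial II (treatment regimens C+D) will contribute to the Aim 3 analysis (n=34"), which is 11 + 23 in the last column of the table. After the table it says "We assumed 80% power and a two-sided alpha of 0.05". The calculation treats the two time points as independent groups, "using a two-sample z-test for proportions with equal sample sizes". On that basis the section expects to "detect a 25% increase in the percentage of infections with antiviral resistance genes (from 5% to 30"%). A closing remark reads: "We note this detectable effect is conservative because it ignores possible correlation within-individuals in the paired outcomes", on the ground that such correlation would raise power.

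SAP 4.1 sets out the testing hierarchy. Its second level reads "Key secondary endpoints (alpha = 0.025 shared") and has two members, inflammation control and "Antiviral resistance mutations". The rule inside each level is "Holm-Bonferroni correction within each family", and secondary endpoints are tested only once the primary endpoints are significant.

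SAP 6.2 (Aim 3) plans a within-patient analysis: a linear binomial model with a fixed effect for each participant, described as similar to McNemar's test. Protocol 8.2 describes the Aim 3 calculation without giving an alpha, a power or a detectable effect, and refers to the SAP.

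**The concern.** The power statement and the testing rule use different significance levels. With two endpoints sharing 0.025 under Holm, resistance is declared significant if its p-value is at most 0.0125, or at most 0.025 when inflammation control has already been rejected. Nothing in either document gives Aim 3 a level of 0.05. The Trial I and Trial II calculations in the same section use 0.05/2, the level that SAP 4.1 gives them, so Aim 3 is the exception.

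What is at stake is how a null result is read. Resistance is part of the SAP's explanation for expecting fewer recurrences on placebo in Trial II. If the resistance comparison is not significant, readers will take it as the outcome of a test with a 20% chance of missing a 25-point rise. Under the SAP's own formula that chance is 31% to 41% at the assigned levels, before the gate is counted.

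**Working it through.** **Inputs.** From SAP 3.3: n = 34 at each time point, p1 = 0.05, p2 = 0.30, two-sided, two-sample z-test. From SAP 4.1: alpha 0.025 for the family, two endpoints, Holm, hence 0.025/2 = 0.0125 at the first step and 0.025 at the second. SAP 4.1 does not state sidedness for this family. Two-sided is assumed, because the section opens with a two-sided alpha and the Aim 3 calculation is two-sided.

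**Step 1: reproduce the stated figure.** Pooled two-sample z-test:

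power = Φ{ [ (p2 − p1)·√n − z·√(2·p̄(1 − p̄)) ] / √( p1(1 − p1) + p2(1 − p2) ) }, with p̄ = 0.175 and z the two-sided critical value.

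- (p2 − p1)·√n = 0.25 × √34 = 1.4577
- √(2 × 0.175 × 0.825) = 0.5374
- √(0.0475 + 0.21) = 0.5074

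At alpha 0.05, z = 1.960, so power = Φ[(1.4577 − 1.0532)/0.5074] = Φ(0.797) = 78.7%. The rate detectable with 80% power is 30.5%. The SAP's 80% and 30% are reproduced to rounding.

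**Step 2: same formula at the assigned levels.**

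| Two-sided alpha | z | Power, 5% v 30%, n = 34 | Rate detectable at 80% power | n needed for 80% at 5% v 30% |
|---|---|---|---|---|
| 0.05 (SAP 3.3) | 1.960 | Φ(0.797) = 78.7% | 30.5% | 36 |
| 0.025 (Holm, second step) | 2.241 | Φ(0.499) = 69.1% | 34.1% | 43 |
| 0.0125 (Holm, first step) | 2.498 | Φ(0.228) = 59.0% | 37.4% | 51 |

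The arcsine form gives 83%, 75% and 66%; the unpooled form gives 82%, 74% and 65%. Every version is below 80% at both assigned levels.

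**Step 3: the paired comparison.** McNemar power for 34 pairs was found by enumerating the discordant pairs. The documents give no within-patient correlation, so the two ends of the non-negative range are assumed:

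- Zero correlation: gain of resistance 0.30 × 0.95 = 0.285; loss 0.05 × 0.70 = 0.035.
- Maximum positive correlation: gain 0.25; loss 0.

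| Two-sided alpha | Asymptotic or mid-p McNemar, zero to maximum | Exact McNemar, zero to maximum |
|---|---|---|
| 0.05 | 79% to 95–98% | 70% to 89% |
| 0.025 | 70% to 89% | 60% to 78% |
| 0.0125 | 57% to 78% | 47% to 64% |

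All figures in both steps are conditional on passing the primary gate. Unconditional power cannot be higher.

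**The case against.** The strongest reply is that the z-test is only a planning approximation. The analysis is paired, positive correlation adds power, and the SAP says so. Much of this stands, and it rules out three stronger readings that a reader might infer.

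- **That the true power of Aim 3 is 59–69%.** This is the power of the unpaired planning formula at the assigned alphas. The planned paired test has a range of power that depends on the correlation and the test form.
- **That 80% power cannot be reached at the assigned levels.** Asymptotic or mid-p McNemar reaches 89% at 0.025 with maximum correlation. A Wald test of the paired difference, which may be closer to the SAP 6.2 model, gives 79% at 0.025 and 70% at 0.0125 with zero correlation, and 95% and 89% at the maximum. Wald tests can be liberal with 34 pairs, so this is not a basis for planning, but it excludes the absolute claim.
- **That the remark about conservatism is wrong even at 0.05, because exact McNemar has only 70% power at zero correlation.** The SAP does not specify an exact test, and the shortfall comes from the discreteness of that test. Like for like, asymptotic McNemar at 0.05 gives 79% at zero correlation against 78.7% for the z-test, and rises with positive correlation as the SAP says.

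Two further points are fair. If the secondary 0.025 were meant as one-sided, the z-test would again give 78.7%, but only at the second Holm step; at one-sided 0.0125 it is 69.1%. The status of Aim 3 is also unsettled: Protocol section 3 lists it among primary objectives, while SAP 6.2 calls the analysis observational. The conflict could therefore be resolved by changing SAP 4.1 instead of SAP 3.3.

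**Conclusion.** The inconsistency is real and is in the text. SAP 3.3 claims 80% power at 0.05; SAP 4.1 assigns 0.0125 or 0.025. By the SAP's own formula the stated power is too high by about 10 points at 0.025 (78.7 − 69.1 = 9.6) and about 20 at 0.0125 (78.7 − 59.0 = 19.7). The detectable rate is about 34% or 37%, not 30%. For the paired analysis the loss may be smaller or larger, and how much pairing recovers cannot be settled without a correlation and a named test.

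The statement that positive correlation would add power is correct. It does not make the 5% to 30% effect conservative at the assigned alpha unless a correlation is given that makes up the loss.

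This rests on a two-sided reading of the secondary family and on the planning values of 34 patients, 5% and 30%. Aim 3 does not drive the sample size (the 34 follow from 117 enrolled), so no primary inference is affected. It is a reporting and interpretation error that should be corrected.

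**What to change.** Choose one of two changes to the SAP.

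1. If Aim 3 stays in the controlled family, restate its power or detectable effect in SAP 3.3 at 0.0125 and 0.025. Preferably use a paired calculation with a stated discordance or correlation and a named test form. If the unpaired formula is kept, give 59% and 69% power, or detectable rates of about 37% and 34%, and label them as figures from that formula. Say that they are conditional on the primary gate, and state the sidedness of the secondary family in SAP 4.1.
2. If Aim 3 is meant to be tested at a nominal 0.05, remove it from the key secondary family in SAP 4.1 and say that the test is outside the family-wise error control. The calculation in SAP 3.3 can then stand.

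Under the first option, keep the sentence about correlation adding power, but call the effect conservative only if a stated correlation supports it. The Protocol needs no numerical change, since it gives no Aim 3 alpha or power. The cost is wording, plus a less favourable figure under the first option or a weaker inferential claim under the second. Enrolment and conduct stay the same.
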